# 12.1. Extent of Exposure

Extent of exposure to GSK2849330 will be captured in the listing of study treatments. The listing will be sorted by part, treatment group, centre, and subject ID. It will include start and stop dates, times of treatment administration (infusion start and stop times), number of days on study, dose, number of days on study treatment, and dose deviation.

Exposure to GSK2849330 and duration on treatment will be summarized for all subjects by treatment dose. Cumulative dose, number of weeks on study treatment and duration on treatment will be included in the summary of exposure to IP. Duration on treatment is defined as days from the first dose to the last dose, regardless of dose interruption. In addition to mean, median, min and max, duration on treatment will also be summarized in the following categories: < 4 weeks, 4-8 weeks, 8-12 weeks, and  $\geq$ 12 weeks.

All the dose reductions, dose escalations, missed doses and dose delays will be listed separately.

It is expected that deviations from planned therapies may occur and therefore a listing of planned and actual treatments will be produced.

A horizontal bar graph of duration of treatment will be produced that displays duration of treatment in weeks by primary tumour type and initial dose for each subject.

# 12.2. Adverse Events

Adverse events (AEs) will be graded according to the CTCAE, Version 4.0. Adverse events will be coded to the preferred term (PT) level using the Medical Dictionary for Regulatory Affairs (MedDRA dictionary).

The relationship between MedDRA SOC, PT, and Verbatim Text will be displayed.

An overview summary of AEs, including counts and percentages of subjects with any AE, AEs related to study treatment, AEs leading to permanent discontinuation of study treatment, AE leading to dose reductions, AEs leading to dose interruptions, SAEs, SAEs related to study treatment, fatal SAEs, and fatal SAEs related to study treatment will be produced.

The following two types of summaries for AEs and drug related AEs will be provided:

- Summary of all AEs by frequency, which is a summary of the number and percentage of subjects with all treatment emergent AEs. Adverse events will be grouped by preferred term and sorted in descending order based on total incidence in all treatment groups.
- Summary of all AEs by maximum toxicity grade, which is a summary of the number and percentage of subjects with all treatment emergent adverse events by intensity or grade. Relevant treatment emergent adverse events will be grouped by the preferred term, and sorted in descending order based on total incidence in all treatment groups.

Treatment emergent AE is defined as adverse events which occur or worsen on or after date and time of first dose of investigational product.

A study treatment-related AE is defined as an AE for which the investigator classifies the relationship to study treatment as "Yes". A worst case scenario approach will be taken to handle missing relatedness data, i.e. the summary table will include events with the relationship to study treatment as 'Yes' or missing. The summary table will be displayed in descending order of total incidence by PT only.

All AEs will be listed. Additionally, a listing of subject IDs for each individual AE will be produced.

A listing of adverse events recorded as dose-limiting toxicities will be provided.

Listing of adverse events for subjects with grade 3 or higher AEs will be provided. In addition, a summary table of non-serious adverse events by system organ class and preferred term with occurrences  $\geq 5\%$  will be generated.

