2.2. Part 2: Molecularly Defined Tumor Histology Groups

Objective	Endpoint
Primary	

 To evaluate the safety of GSK2849330 in a larger population of subjects in molecularly-defined tumor histology groups at the dose regimen(s) recommended for further exploration in Part 1. 	
 AEs, SAEs, DLTs, and changes in laboratory values, ECGs, and vital signs.
Secondary	

 To evaluate preliminary evidence of clinical benefit. To further characterize target engagement and PD effects of GSK2849330. To further characterize the PK of GSK2849330. To characterize the relationship between GSK2849330 PK, markers of target engagement, and/or PD markers. To evaluate the immunogenicity of GSK2849330 following IV administration. 	
 ORR, tumor markers, and other measures of clinical benefit. Total and phospho-HER3 from tumor tissue. PK parameter values for GSK2849330. PK parameter values for GSK2849330 Antibodies to GSK2849330 in serum
Exploratory	

 To explore additional measures of clinical benefit. To further characterize target engagement and PD effects of GSK2849330. To explore relationship between pre-treatment HER3 or HER3/NRG1 expression levels and clinical outcome. 	
 Progression free survival (PFS), ORR according to immune-related response criteria (irRc) and modified Response Evaluation Criteria in Solid Tumors mRECIST where applicable, and other tumor markers and measures of clinical benefit Pre- and post- treatment biomarkers (cells, proteins, RNA and/or DNA) from circulation and/or tumor tissue. Pre-treatment HER3 expression or HER3 and NRG1 levels, efficacy outcome parameters.

 To identify molecular features potentially predictive of response to GSK2849330. 	
 Prediction analysis of biomarkers (cells, DNA, RNA or protein) in tumor, and/or circulation with efficacy endpoints.

Objective	Endpoint
Pharmacogenetic (PGx) Exploratory	

 To investigate the relationship between genetic variants in candidate genes and safety, tolerability, PK, PD, and/or efficacy of GSK2849330. 	
 Genetic variations in selected candidate genes, such as the FCγ receptor family, safety, tolerability, PK, PD, and/or efficacy endpoints.

[figure not shown]

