3.3.1. Dose-Limiting Toxicity

An event will be considered a DLT if it occurs within the first 4 weeks (28 days) of treatment, and meets one of the following criteria unless it can be clearly established that the event is unrelated to treatment:

- a. Grade 3 or greater non-hematologic toxicity as described in Common National Cancer Institute-Terminology Criteria for Adverse Events (NCI-CTCAE) version 4.0 [NCI, 2009] that cannot be controlled with routine supportive measures (e.g., antiemetics, antidiarrheals, antihistamines).
- b. Grade 4 neutropenia lasting >5 days.
- c. Febrile neutropenia, of any grade or duration as defined by NCI-CTCAE version 4.0 [NCI, 2009].
- d. Grade 4 thrombocytopenia, or Grade 3 thrombocytopenia associated with bleeding.
- e. Alanine aminotransferase (ALT) >3x upper limit of normal (ULN) with bilirubin >2x ULN.
- f. Any Grade 2 or greater NCI-CTACAE version 4.0 [NCI, 2009] toxicity that in the judgment of the investigator and GSK Medical Monitor, would be considered dose-limiting.
- g. Grade 3 or greater decrease in left ventricular ejection fraction (LVEF).

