5. STUDY POPULATION

5.1. Number of Subjects

The number of dose levels and the level at which the MTD is reached cannot be determined in advance. An adequate number of subjects will be enrolled into the study to establish the recommended dose(s) for further study. It is estimated that approximately 13 subjects will be enrolled in Part 1 dose escalation if there are no DLTs observed; if there are any DLTs observed, more than 13 subjects can be enrolled in dose escalation. Up to an additional 21 subjects with evaluable pre- and on-treatment paired biopsies can be enrolled for the purpose of the PK/PD cohorts in Part 1. Therefore, up to approximately 34 subjects may be enrolled into Part 1 (dose-escalation and PK/PD cohorts) of the study; however, additional dose escalation cohorts may be enrolled to allow for further evaluation of additional dose levels/regimens if warranted.

In Part 2 of the study, there will be at least 4 molecularly-defined tumor histology groups. It is estimated that a minimum of 12 subjects will be enrolled in each group with a maximum of approximately 30 subjects if futility criteria are not met. Therefore, approximately 120 subjects may be enrolled in Part 2 and approximately 154 subjects may be enrolled in the entire study; however, this number will be considerably fewer if futility conditions are met for any group in Part 2 (see Section 3.4, Section 13.2.2, and Section 13.6.2). Additional groups of tumor histologies predicted to be sensitive to the study drug based on emerging nonclinical or clinical data may be added to Part 2.

In Part 1 (dose escalation) of the study, if subjects prematurely discontinue for reasons other than toxicity, additional subjects may be enrolled as replacement subjects and assigned to the same treatment cohort at the discretion of the Sponsor in consultation with the investigator. Subjects may also be replaced in Part 2 of the study for the purpose of testing futility or to facilitate collection of sufficient tumor biopsies for exploratory analyses.

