13.7.2.2. Adverse Events

AEs will be coded using the standard MedDRA and grouped by system organ class. AEs will be graded by the investigator according to the NCI-CTCAE, (version 4.0) [NCI, 2009]. Summaries of the number of toxicity grades for both laboratory and non-laboratory data will be presented.

Events will be summarized by frequency and proportion of total subjects, by system organ class and preferred term. Separate summaries will be given for all AEs, treatment-related AEs, SAEs and AEs leading to discontinuation of study treatment. AEs, if listed in the NCI-CTCAE (version 4.0) [NCI, 2009] will be summarized by the maximum grade. Otherwise, the AEs will be summarized by maximum intensity.

The incidence of deaths and the primary cause of death will be summarized.

DLTs will be listed for each subject and summarized by dose cohort according to IDSL standards.

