# 7.1. Data Display Treatment and Other Subgroup Descriptors

Treatment groups with the same dose and the same administration frequency will be combined in final analyses as displayed in the table below. All data will be summarized or listed by the treatment group except PK concentration data, which will be listed by part and dose cohort.

Treatment	Treatment Description	Treatment Label / Column Header
Code		
1	Part 1 DE Cohort: 1.4 mg/kg weekly	Part 1 Cohort: 1.4 mg/kg weekly
2	Part 1 DE Cohort: 3 mg/kg every 2 weeks	Part 1 Cohort: 3 mg/kg every 2 weeks
3	Part 1 DE & PK/PD Cohort: 10 mg/kg every 2 weeks	Part 1 Cohort: 10 mg/kg every 2 weeks
4	Part 1 DE & PK/PD Cohort: 30 mg/kg every 2 weeks	Part 1 Cohort: 30 mg/kg every 2 weeks
5	Part 1 DE & PK/PD Cohort: 30 mg/kg weekly	Part 1 Cohort: 30 mg/kg weekly
6	Part 1 PK/PD Cohort: 3 mg/kg weekly	Part 1 Cohort: 3 mg/kg weekly
7	Part 2 Expansion Cohort: 30 mg/kg	Part 2 Cohort: 30 mg/kg

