# 12. SAFETY ANALYSES

Unless otherwise specified, all the safety analyses will be based on the All Treated population as defined in Section 6 and summaries will include all events or assessments collected during the study.

The lists of displays for safety analyses, including population to use for each display, are shown in Section 19 of the RAP.

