## Tables

No.	Population	IDSL No. / Example Shell	Title	Programming Notes	Deliverable
11.1	All Treated	OEX1	Summary of Exposure to GSK2849330	Including Ave. Dose, Cum. Dose, Time on study treatment (weeks)	SAC
11.2	All Treated	OEX3a	Listing of Exposure to GSK2849330		SAC
11.3	All Treated	IP2	Listing of Investigational Product Compliance	If IPCOMP data is available	SAC
11.4	All Treated		Summary of Dose Reduction	arenv/arprod/gsk2636771/p3b1157 17/sac/drivers/t_dosredgsk.sas	SAC
11.5	All Treated		Summary of Dose Interruption	arenv/arprod/gsk2636771/p3b1157 17/sac/drivers/t_dosintgsk.sas	SAC
11.6	All Treated	AE3	Summary of All Adverse Events by Frequency		SAC
11.7	All Treated	OAE07	Summary of All Adverse Events by Maximum Grade		SAC
11.8	All Treated	AE3	Summary of Drug-Related Adverse Events		SAC

No.	Population	IDSL No. / Example Shell	Title	Programming Notes	Deliverable
11.9	All Treated	OAE07	Summary of Drug-Related Adverse by Maximum Grade		SAC
11.10	All treated	AE3	Summary of Serious adverse events by Frequency		SAC
11.11	All treated	OAE07	Summary of Serious adverse events by Maximum Grade		SAC
11.12	All treated		Adverse Events Overview	arenv/arprod/gsk2636771/p3b 115717/sac/drivers/t_ae_overv iew.sas	SAC
11.13		AE8	Listing of Fatal Serious Adverse Events		SAC
11.14	All treated	DL3	Listing of Dose-Limiting Toxicities	For DE cohorts only	SAC
11.15	All treated	AE8	Listing of subjects with Grade 3 or Higher Adverse Events		SAC
11.16	All treated	AE3	Summary of Adverse Events of Special Interest	See Section 12.3	SAC
11.17	All treated	AE8	Listing of Cardiovascular Adverse Events	See RAP Section 12.4	SAC
11.18	All treated	AE8	Listing of AEs leading to dose delay or reduction or interruption		SAC
11.19	All treated	AE8	Listing of Adverse Events Leading to Permanent Discontinuation of Study Treatment or Withdrawal from the Study		SAC
11.20	All treated	DTH3	Listing of deaths	including time from last dose	SAC
11.21	All treated		Summary of Non-serious Adverse Events by Preferred Team with Occurrences >=5%	/arenv/arprod/gsk2636771/p3 b115717/sac/drivers/t_ae_non _ser.sas	SAC
11.22	All treated		Summary of Serious Adverse Events by Preferred Term Including Drug-related Status and Fatal Status	/arenv/arprod/gsk2636771/p3 b115717/sac/drivers/t_ae_ser_ 2.sas	SAC
11.23	All treated	OLB6	Summary of Clinical Chemistry Toxicity Grade Change from Baseline		SAC

No.	Population	IDSL No. / Example Shell	Title	Programming Notes	Deliverable

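### The SAP drops the protocol's DLT summary, and its only DLT display is a listing whose note limits it to dose-escalation cohorts, so this primary endpoint is under-reported for PK/PD and Part 2 subjects.

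*SAP*

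**What the plan says.** Protocol 13.7.2.2: "DLTs will be listed for each subject and summarized by dose cohort according to IDSL standards". Protocol 13.7.2, under the All Treated Population, also promises both a listing and a summary, with no limit by part or type of cohort.

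DLTs are a primary endpoint in Protocol 2.1, whose heading covers the escalation and PK/PD cohorts together. They are again in Protocol 2.2 for Part 2: "AEs, SAEs, DLTs, and changes in laboratory values, ECGs, and vital signs". SAP 2 repeats both.

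SAP 12.2 offers one output: "A listing of adverse events recorded as dose-limiting toxicities will be provided". Its adverse event overview has no DLT row. SAP 12 sends the reader to the display list: "The lists of displays for safety analyses, including population to use for each display, are shown in Section 19 of the RAP". There, in SAP 19.1.3, listing 11.14 is the only DLT display. Its population column covers all treated subjects and its programming note reads "For DE cohorts only".

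Protocol 13.7 requires departures from its analysis plan to be documented in the RAP (the SAP) and the study report. The SAP has no such entry for DLTs. SAP 8.1 deals only with departures from the RAP itself, and the early stop is invoked in SAP 11 for efficacy alone.

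**The concern.** The protocol promised two outputs. The SAP drops one, the summary, and narrows the other through a programming note. A programmer working from SAP 19 is likely to follow the note.

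A primary safety endpoint would then have no count by dose anywhere in the final report, and two regimens would have no DLT display. SAP 7.1 also pools escalation and PK/PD subjects under one column header for codes 3, 4 and 5. An escalation-only listing under those headers could suggest that a regimen had no DLT when a PK/PD subject on it did.

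No planned display outside 11.14 is described as showing DLT status, and that status cannot always be inferred from the event. Protocol 3.3.1 criterion (a) depends on whether supportive measures controlled the event. Criterion (f) covers any Grade 2 or greater "toxicity that in the judgment of the investigator and GSK Medical Monitor, would be considered dose-limiting". A Grade 2 DLT need not appear in the listing of Grade 3 or higher events.

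**Working it through.** **1. Coverage by treatment group (SAP 7.1 against listing 11.14 with its note)**

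| Code | Subjects | DLT listing | DLT summary |
|---|---|---|---|
| 1, 2 | Escalation only | Yes | None |
| 3, 4, 5 | Escalation and PK/PD pooled | Depends on how the note is read | None |
| 6, "Part 1 PK/PD Cohort: 3 mg/kg weekly" | PK/PD only | None | None |
| 7 | Part 2 | None | None |

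So 2 of 7 groups have no DLT display on either reading of the note, and 7 of 7 have no DLT summary.

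**2. Planned numbers.** Protocol 5.1 gives about 13 escalation subjects and, as a ceiling, "an additional 21 subjects with evaluable pre- and on-treatment paired biopsies can be enrolled for the purpose of the PK/PD cohorts in Part 1". It gives about 120 subjects in Part 2. The total is 13 + 21 + 4 × 30 = 154, which matches the protocol. In Part 1, PK/PD subjects are at most 21/34 = 62%. SAP 7.1 shows PK/PD subjects in only four regimens (codes 3 to 6). At up to 3 evaluable subjects each (SAP 3) that is 12, and 12/(13 + 12) = 48%; unevaluable subjects could add to it. These are plans. The study stopped early and the documents do not give actual enrolment.

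**3. Chance of an empty listing that misses a DLT (narrow reading of the note)**

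Inputs: 3 escalation and 3 PK/PD subjects (Protocol Table 3), and the three true DLT rates simulated for 30 mg/kg in Protocol Table 14. Assumptions: the rate p is the same in both sets and subjects are independent.

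P(no DLT in 3 escalation subjects and at least one in 3 PK/PD subjects) = (1 − p)³ × [1 − (1 − p)³]

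- p = 0.055: 0.844 × 0.156 = 0.132
- p = 0.25: 0.422 × 0.578 = 0.244
- p = 0.3: 0.343 × 0.657 = 0.225

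The range is about 13% to 24%.

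**4. The extreme case.** An empty listing with all 3 PK/PD subjects having a DLT (3 of 6, or 50%) has probability 0.343 × 0.3³ = 0.343 × 0.027 = 0.009 at p = 0.3. An empty listing with 2 or 3 of the PK/PD subjects affected (at least 33% of 6) has probability 0.343 × (3 × 0.3² × 0.7 + 0.3³) = 0.343 × 0.216 = 0.074 at p = 0.3, and about 0.007 at p = 0.055.

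**The case against.** **The restriction is not settled.** SAP 12.2 contains no limit, and the population column for 11.14 covers all treated subjects. SAP 7.1 says groups with the same dose and frequency are combined, so the note could mean any group containing escalation subjects. This stands in part. SAP 7.1 uses DE and PK/PD as separate labels, which favours the narrow reading, but the text does not decide it. The result for codes 3 to 5 is therefore conditional. Codes 6 and 7 contain no escalation subjects and are left out either way.

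**DLTs may have been meant for escalation only.** Protocol 13.7.2.2 says dose cohort, while 13.5.2 and 13.7.3.2 say cohort or group when Part 2 is included. Protocol 10.1 bars growth factors in the Part 1 DLT observation period but may allow them in the PK/PD cohorts and Part 2, so the neutropenia criteria are not comparable. This is a fair reason to show the sets separately. It does not remove the commitment: 13.7.2 and the endpoint lists are unrestricted, and the 28-day definition in 3.3.1 names no cohort type.

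**The events are not lost.** Criteria (b) to (e) and (g) are objective. Protocol 3.9.4 stops treatment for a toxicity that meets the DLT guidelines, and 3.9.5 reduces the dose in Part 1. Such events should reach displays 11.4, 11.5, 11.12, 11.15, 11.18 and 11.19, none of which has an escalation-only note. This stands. A reader might infer that DLT status can never be rebuilt, but the documents support that doubt only for criteria (a) and (f). The standard listing shells, which might carry a DLT flag, are not in the documents.

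**Conclusion.** The point holds and should be corrected. The SAP omits a DLT summary that the protocol promised, contradicts itself on who is in the only DLT listing, and records no deviation. No group gets a DLT count by dose, and codes 6 and 7 get no DLT display. For codes 3 to 5 the gap exists only if the note means escalation subjects alone. The 13% to 24% then applies at 30 mg/kg, given 3 + 3 subjects, a common rate and independence.

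Three stronger readings are not supported. A reader might take 62% as the share of Part 1 subjects left out, but it is a planning ceiling. A reader might stress that an empty listing is compatible with DLTs in half the subjects, but that has a probability of about 0.9% even at a rate of 0.3. A reader might also infer that escalation decisions were compromised. SAP 4.1 bases those on the N-CRM and a review of all available data, not on listing 11.14.

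**What to change.** First confirm that DLT status was collected for PK/PD and Part 2 subjects. Then:

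1. Delete the programming note on 11.14 so that the listing covers all treated subjects, as its population column already says.
2. Add one DLT summary to SAP 12.2 and 19.1.3: the number of subjects with a DLT in the first 28 days, by SAP 7.1 treatment group. Within codes 3 to 5, show escalation and PK/PD subjects separately, because the growth-factor rules in Protocol 10.1 differ.
3. If DLTs were meant to be assessed only in escalation subjects, say so in the SAP as a deviation from the protocol and correct the endpoints in SAP 2. The promised summary by dose cohort is still needed for those subjects.

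The cost is one deleted note and one small table. If DLT status was not collected outside escalation, the third route applies and the SAP should give that reason.

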### 12.3. Adverse Events of Special Interest

A comprehensive list of MedDRA terms based on clinical review will be used to identify each type of events. Changes to the MedDRA dictionary may occur between the start of the study and the time of reporting and/or emerging data from on-going studies may highlight additional adverse events of special interest, therefore the list of terms to be used for each event of interest and the specific events of interest will be based on the safety review team (SRT) agreements in place at the time of reporting.

The events of special interest include:

- AEs related to infusion reactions, which include new onset fever, myalgia, chills, rigors, nausea, vomiting, malaise occurring during the infusion to 1 hour after the infusion
- AEs related to allergic reaction include dyspnea, edema etc.
- Diarrhea of any grade

Summaries of the number and percentage of subjects with these events will be provided for each type of events separately, if data permit.

Characteristics (e.g. number of occurrences, action taken, grade, etc) of the three type AEs of special interest will be listed.

Listing of cardiovascular adverse events will be provided including the following AEs and SAEs.

- Myocardial infarction/unstable angina
- Congestive heart failure
- Arrhythmias
- Valvulopathy
- Pulmonary hypertension
- Cerebrovascular events/stroke and transient ischemic attack
- Peripheral arterial thromboembolism
- Deep venous thrombosis/pulmonary embolism
- Revascularisation

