3.7.2. Dosage and Administration of Study Treatment(s)

GSK2849330 will be given by IV infusion over a 1-hour period. If an infusion-related reaction occurs during administration, the infusion rate may be reduced or halted at the discretion of the investigator and/or GSK medical monitor, depending on the severity of the symptoms; the subject will receive appropriate medical treatment. When the subject's condition is stable, the infusion may be restarted according to the judgment of the investigator. Upon restart, the infusion rate should be half of the infusion rate at the time the infusion was paused.

Guidance for the monitoring and managing of infusion related reactions and allergic/hypersensitivity reactions, including anaphylaxis, are outlined in Section 3.9.1 and Section 3.9.2.

Subjects should be monitored for at least 1 hour after the completion of the infusion and may be discharged if considered clinically stable and all other study procedures have been completed.

Guidelines for dosage modifications are provided in Section 3.9.4.

The dose of study treatment is discussed in Section 3.3 and Section 3.4.

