3.9. Guidelines for Events of Special Interest and Dose Modifications

The severity of AEs will be graded utilizing NCI-CTCAE, version 4.0 [NCI, 2009]. Guidelines for dose modifications and interruptions for management of common toxicities associated with the study treatment(s) are provided in this section.

In subjects experiencing suspected infusion-related reactions, a whole blood sample for selected cytokines (including but not limited to TNF alpha, IL-6, and tryptase) should be drawn within 24 hours and submitted to the central laboratory for analysis (see SPM for instructions).

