3.9.1. Management of Infusion Reactions

As there is a risk of infusion reactions during administration of IV immunoglobulins, including monoclonal antibodies, subjects will be monitored for signs and symptoms of an infusion-related reaction (including Grade 1 to 2 fever, chills, headache, nausea, malaise) during infusion and for a minimum of 1 hour after the first administration of GSK2849330.

If an infusion-related reaction occurs during administration, the infusion rate may be reduced or halted at the discretion of the investigator and/or GSK medical monitor, depending on the severity of the symptoms and the subject will receive appropriate medical treatment. For subsequent infusions, the investigator may provide premedication with antihistamines, acetaminophen, and/or corticosteroids and may reduce the starting infusion rate.

Treatment may include:

- **Fevers/Myalgia:** Initiate treatment with acetaminophen (paracetamol). If subject's fever does not respond to acetaminophen, consideration should be given to the use of a nonsteroidal anti-inflammatory drug (NSAID) such as indomethacin. Consider pre-medication with acetaminophen for subsequent doses.
- **Chills/rigors:** Use warming blankets as initial intervention; consider IV meperidine (pethidine) if chills persist.
- **Nausea/vomiting:** Consider treatment with 5-HT3 antagonists, prochlorperazine, lorazepam; some agents may cause hypotension and altered mental status; therefore, these agents should be used with caution.

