4. Separate pre-screening consent required for fresh biopsy and fresh biopsy is only collected at pre-screening if archived tissue is not available.
5. Fresh pre- and on-treatment tumor biopsy is optional, but strongly encouraged for dose escalation cohorts; if adequate fresh biopsy tumor tissue is acquired during pre-screening, then this does not need to be repeated during the screening period. Archival tumor tissue is not acceptable to serve as pre-treatment tumor tissue.

6. Tumor biopsy is optional on Day 15 for dose escalation cohort subjects and required for the PK/PD cohorts. Biopsy must be collected prior to study treatment administration on Day 15 dose (pre-dose).
7. Collected at progression. Tumor biopsy is optional and only collected for subjects with disease progression on study treatment. The tumor specimen may be collected at any time after study treatment discontinuation, but must occur prior to the start of any subsequent anticancer therapy.
8. Perform only in women of child-bearing potential. Serum pregnancy test should be conducted at the Screening, Follow-up, and Post-study visits. Urine pregnancy test should be conducted pre-dose on Day 29 and every 4 weeks from Day 29 in the continuation phase of the study.
9. If the screening visit was completed within 72 hours of the first dose, this assessment does not need to be repeated on Day 1.
10. Collect at pre-dose and at 1, 2, 4, and 6 hours after the start of the first infusion.
11. ECHO is preferred; however, if echocardiography is not available, or if reliable echocardiographic analysis of LVEF is unable to be obtained due to technical factors, a MUGA scan may be performed. Regardless, the method used at Baseline should be used for the remaining assessments in the study. Assessments should be performed more frequently than every 8 weeks if clinically indicated.

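### SAP 12.3 prints a one-hour onset limit for infusion reactions where the protocol sets only a one-hour minimum of monitoring, so later suspected reactions can miss the special-interest displays

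*SAP*

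**What the plan says.** SAP 12.3 names three types of event of special interest. The first is AEs related to infusion reactions, said to include "new onset fever, myalgia, chills, rigors, nausea, vomiting, malaise occurring during the infusion to 1 hour after the infusion". The section opens with "A comprehensive list of MedDRA terms based on clinical review will be used to identify each type of events". It adds that the terms and the specific events of interest "will be based on the safety review team (SRT) agreements in place at the time of reporting". The results go to Table 11.16 (SAP 19.1.3) and ICH Listing 23 (SAP 19.1.7).

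The protocol uses the hour differently. Section 3.9.1 has subjects watched for infusion reactions, and describes the symptoms and the timing as follows: "including Grade 1 to 2 fever, chills, headache, nausea, malaise) during infusion and for a minimum of 1 hour after the first administration". Section 3.7.2, without restricting itself to the first dose, says "Subjects should be monitored for at least 1 hour after the completion of the infusion". Section 3.9 requires a blood draw: "In subjects experiencing suspected infusion-related reactions, a whole blood sample for selected cytokines", to be taken within 24 hours. None of these sections says how soon after the infusion a reaction must start.

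For Day 1 vital signs and ECG, footnote 10 to Table 7 says "Collect at pre-dose and at 1, 2, 4, and 6 hours after the start of the first infusion". Footnote 10 to Table 12 gives the same times for vital signs in Part 2.

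**The concern.** A minimum observation time has become, in the SAP, the outer edge of the event description. The two serve different purposes. The first says how long a subject must be watched. The second says which events belong to a category. If the SAP sentence is programmed as printed, a subject with chills and rigors starting 3 hours after the infusion could have the cytokine sample drawn and premedication at the next dose, and still not count as an infusion reaction in the one summary meant to give that incidence by treatment group. The set of subjects with a safety-cytokine draw and the set in Table 11.16 could then differ, and SAP 12.3 does not say how to reconcile them. This is a first-in-human antibody engineered for stronger ADCC and CDC (protocol 1.2.1), so infusion-reaction incidence is a figure readers will look for.

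Two smaller points go with it. Headache is in the protocol's monitoring sentence but not among the SAP's printed symptoms. The protocol also leaves it unclear whether the post-infusion hour applies to every infusion (as 3.7.2 reads) or only the first (3.9.1), whereas the SAP window is not restricted to the first infusion.

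**Working it through.** The plan states no figure to reproduce. The check compares the passages and converts clock times.

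**Onset window against scheduled checks.** Inputs: planned infusion of 1 h (protocol 3.7.2); checks at 1, 2, 4 and 6 h after the start of the first infusion (footnote 10 to Tables 7 and 12); SAP window closing 1 h after the end of the infusion (SAP 12.3).

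Hours after end = hours after start − infusion duration.

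| Check (h after start) | h after end of a 1 h infusion | Inside SAP window (≤ 1 h)? |
|---|---|---|
| 1 | 1 − 1 = 0 | yes |
| 2 | 2 − 1 = 1 | yes, at the edge |
| 4 | 4 − 1 = 3 | no |
| 6 | 6 − 1 = 5 | no |

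So 2 of the 4 scheduled checks after the start fall beyond the printed window. If an infusion is slowed to a duration of d hours, the 4 h check is outside when 4 − d > 1, that is d < 3, and the 6 h check is outside when 6 − d > 1, that is d < 5. The result does not depend on the infusion lasting exactly 1 h.

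**Trigger for the cytokine sample.** Protocol 3.9 makes suspicion the trigger. Its 24 hours is the time allowed for the draw. A reaction starting after the SAP window closes therefore still triggers the sample.

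**Does the safety review team deferral remove the limit?** SAP 12.3 hands over the MedDRA terms and the specific events of interest. A MedDRA term carries no onset time, and the sentence does not mention the window. The deferral can change which symptoms count. It does not expressly change when they must start.

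**Symptoms side by side.**

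| Symptom | Protocol 3.9.1 monitoring sentence | SAP 12.3 |
|---|---|---|
| Fever, chills, nausea, malaise | named | named |
| Headache | named | not named |
| Myalgia, rigors, vomiting | not named (they appear in the 3.9.1 treatment bullets) | named |

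Four of the five symptoms in the protocol's sentence are carried over. Headache is the exception.

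**Where a late reaction would still be seen.** SAP 12.2 lists every AE and summarises AEs by frequency and by maximum grade, overall and drug-related (Tables 11.6 to 11.9). SAP 12.5 lists AEs leading to dose interruption, delay or reduction. These displays show fever or chills under their own preferred terms. They do not give an infusion-reaction incidence.

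**The case against.** The strongest reply is that SAP 12.3 is not a closed definition. It introduces the symptoms as things that are included, says a comprehensive term list will identify the events, and leaves terms and events of interest to the safety review team. This stands for symptoms: a reader might infer that headache will never be counted, and the text does not support that. It is weaker for timing. One can argue that the window is illustrative too, because it sits in the same clause, but nothing says so, and a programmer has no other window to use. The accurate description is a printed limit that the deferral does not expressly relax.

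A second reply is that the Day 1 checks are general first-dose readings, not infusion-reaction monitoring. Footnote 10 to Table 7 covers ECG as well as vital signs, and protocol 7.3.3 says temperature need not be repeated on days with several readings unless clinically indicated. This also stands in part. The 4 h and 6 h checks need not detect a fever. They show only that the protocol has scheduled readings after the SAP window closes. The argument rests mainly on the unlimited trigger in 3.9.

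A third reply is that the monitoring expressly tied to infusion reactions is also at least one hour, so SAP and protocol meet at that minimum. That is correct, and the gap opens only for reactions that appear or are reported later.

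Finally, protocol 3.7.2 and 3.9.1 can both be followed at once. They are ambiguous together rather than incompatible. A site reading 3.9.1 alone could still conclude that later infusions need no observed hour.

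**Conclusion.** The point holds as a mismatch between the SAP's event description and the protocol's handling of suspected reactions, and it should be fixed. The effect is confined to Table 11.16 and ICH Listing 23. With a 1-hour infusion, two of the four scheduled Day 1 checks after the start lie beyond the printed window. How many events are affected cannot be derived from the documents, because neither gives an expected timing of reactions. The conclusion assumes that the window will be applied as printed.

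Three stronger readings should be resisted:

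- A reader might infer that the primary safety endpoint is under-reported. It is not: that endpoint is AEs, SAEs, DLTs and changes in laboratory values, ECGs and vital signs (protocol 2.1 and 2.2), and a late reaction remains in the general AE displays.
- A reader might take the 24 hours in protocol 3.9 as the protocol's own onset window and compare the SAP window with it. It is a deadline for drawing blood.
- A reader might take the 24-hour wait after the first subject of a cohort (protocol 3.3) in the same way. It concerns unanticipated acute toxicity in general and does not define an infusion reaction. Neither passage supports a 24-hour onset rule in the SAP.

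**What to change.** In SAP 12.3:

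1. Count as an infusion reaction, in addition to the printed description, any AE the investigator recorded or managed as a suspected infusion-related reaction, whatever its onset time. Possible markers are an infusion slowed or halted for a reaction, or a safety-cytokine sample drawn. The documents do not show whether the case report form has a direct field for suspicion, so the SAP should name the data source.
2. Show the events with onset within 1 hour after the infusion as a separate row of Table 11.16.
3. Add headache, or state that the printed symptoms are examples and that the safety review team's list governs.

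In the protocol, 3.7.2 and 3.9.1 must be reconciled on whether post-infusion monitoring applies to every infusion or only the first. Which of the two applies is for the sponsor to decide.

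The cost is a few lines of SAP text, one table row and one protocol clarification. The small downside is that some nonspecific later events will enter the special-interest table. The within-one-hour row lets a reader see how many there are.
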